## 1. VERSION HISTORY

**Table 1. Summary of Changes**

Version/ Date	Associated Protocol Amendment	Rationale	Specific Changes
1 16 October 2020	Original 28 Aug 2020	N/A	N/A

## 2. INTRODUCTION

This statistical analysis plan (SAP) provides the detailed methodology for summary and statistical analyses of the data collected in Study C4491004. This document may modify the plans outlined in the protocol; however, any major modifications of the primary endpoint definition or its analysis will also be reflected in a protocol amendment.

### 2.1. Study Objectives, Endpoints, and Estimands

The followings are objectives and endpoints in this study. Estimand framework is not applied to this phase 1 study.

Objectives	Endpoints
Primary:	Primary:

 
To characterize the PK of vupanorsen following 80 and 160 mg single subcutaneous dose in healthy Chinese adults.
 
	
 
Vupanorsen plasma PK parameters: <math>AUC_{24h}</math>, <math>AUC_{48h}</math>, <math>AUC_{last}</math>, <math>C_{max}</math>, <math>AUC_{inf}</math>, <math>T_{max}</math>, <math>t_{1/2}</math>, <math>CL/F</math> and <math>Vz/F</math>, as data permit.
 

Secondary:	Secondary:

 
To evaluate the safety and tolerability of vupanorsen following 80 and 160 mg single subcutaneous dose in healthy Chinese adults.
 
To characterize the PD effects of vupanorsen following 80 and 160 mg single subcutaneous dose in healthy Chinese adults.
 
	
 
Adverse events, clinical safety laboratory tests (serum chemistry, hematology, urinalysis, coagulation), vital signs (BP, PR), physical examination findings, 12-lead ECGs.
 
Percentage change from baseline in ANGPTL3 on Day 2, Day 3, Day 8, Day 15, Day 30, Day 60 and Day 90.
 
Percentage changes from baseline in Lipid Panel on Day 2, Day 3, Day 8, Day 15, Day 30, Day 60 and Day 90,
 

	
including fasting TG, LDL-C, HDL-C, VLDL-C, non-HDL-C, and TC.
 
 
Percentage changes from baseline in ApoA-I, ApoB total (including ApoB-48, ApoB-100), and ApoC-III on Day 15, Day 60 and Day 90.
 

--	--

## 2.2. Study Design

This is a Phase 1, randomized, parallel-cohort, open-label study to characterize the PK, PD safety and tolerability of vupanorsen following 80 mg and 160 mg single subcutaneous dose in healthy Chinese adults with fasting triglyceride  $\geq$ 90 mg/dL. Approximately 18 participants will be enrolled in this study (N=9 for each cohort) with the goal of attaining approximately 8 evaluable participants in each cohort for a total of 16 evaluable participants.

The total duration of participation in this study is approximately 118 days, including a screening period of up to 28 days to confirm eligibility and a follow-up period of approximately 90 days. Eligible participants will progress to admission to the clinical research unit on Day -1 for a 4-day (3-night) inpatient stay. Participants enrolled will receive a single 80 mg (cohort 1) or 160 mg (cohort 2) subcutaneous dose of vupanorsen on Day 1. Following discharge on Day 3, participants will return for an on-site post-treatment evaluation on Days 8, 15, 30, 60 and 90.

Participants who discontinue prior to completion of the study for non-safety related reasons may be replaced, at the discretion of the principal investigator and sponsor study team.

## 3. ENDPOINTS AND BASELINE VARIABLES: DEFINITIONS AND CONVENTIONS

### 3.1. Primary Endpoint(s)

Primary endpoints are following vupanorsen plasma PK parameters:

**Table 2. Plasma Vupanorsen Pharmacokinetic Parameters**

Parameter	Definition	Method of Determination
Cmax	Maximum plasma concentration	Observed directly from data
Tmax	Time at which Cmax occurred	Observed directly from data as time of first occurrence
AUC24h	Area under the concentration-time profile from time 0 to 24 hour post-dose	Linear/log trapezoidal method
AUC48h	Area under the concentration-time profile from time 0 to 48 hour post-dose	Linear/log trapezoidal method

**Table 2. Plasma Vupanorsen Pharmacokinetic Parameters**

Parameter	Definition	Method of Determination
AUC last	Area under the concentration-time profile from time 0 to the time of the last quantifiable concentration (C last )	Linear/log trapezoidal method
AUC inf *	Area under the concentration-time profile from time 0 extrapolated to infinite time	AUC last + (C last */kel), where C last * was the predicted serum concentration at the last quantifiable time point estimated from the log-linear regression analysis
t 1/2 *	Terminal elimination half-life	Loge(2)/kel, where kel was the terminal phase rate constant calculated by a linear regression of the log-linear concentration-time profile
CL/F*	Apparent clearance	Dose/AUC inf
V z /F*	Apparent volume of distribution	Dose/(AUC inf *kel)

\* If data permitted.

Pharmacokinetic parameters will be calculated using an internally validated software system, electronic non-compartmental analysis (eNCA, version 2.2.4 or higher).

### 3.2. Secondary Endpoint(s)

#### 3.2.1. Safety Endpoints

Safety endpoints are:

- Adverse events (AE);
- Clinical safety laboratory measurements, including serum chemistry, hematology, urinalysis, and coagulation;
- Vital signs, including blood pressure (BP) and pulse rate (PR);
- Physical examination findings;
  - Any untoward findings identified on physical examinations conducted during the active collection period will be captured as AEs, if those findings meet the definition of an AE.
- 12-lead ECGs.

The details of the safety endpoints are described in Section 3.5.

### **3.2.2. Pharmacodynamics Endpoints**

PD endpoints are:

- Percentage change from baseline in ANGPTL3 on Day 2, Day 3, Day 8, Day 15, Day 30, Day 60 and Day 90;
- Percentage changes from baseline in Lipid Panel on Day 2, Day 3, Day 8, Day 15, Day 30, Day 60 and Day 90, including fasting TG, LDL-C, HDL-C, VLDL-C, non-HDL-C, and TC;
- Percentage changes from baseline in ApoA-I, ApoB total (including ApoB-48, ApoB-100), and ApoC-III on Day 15, Day 60 and Day 90.

### **3.3. Other Endpoint(s)**

Not applicable.

### **3.4. Baseline Variables**

There are no baseline variables to be used as covariates or stratification factors in this study.

The demographic data will include age, sex, weight, body mass index. Baseline variables are those collected on Day 1 prior to dosing or last measurement before Day 1.

### **3.5. Safety Endpoints**

#### **3.5.1. Adverse Events**

All events that start on or after the first dosing day and time/start time, if collected, but before the last dose plus the lag time as defined in the protocol will be flagged as Treatment-Emergent Adverse Events (TEAEs). If an AE starts on the same day as the first dose date, it will be considered treatment emergent unless the case report form data indicates otherwise via explicitly recording time for AE onset and treatment dosing.

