8.3.1. Time Period and Frequency for Collecting AE and SAE Information

The time period for actively eliciting and collecting AEs and SAEs (“active collection period”) for each participant begins from the time the participant provides informed consent, which is obtained before the participant’s participation in the study (ie, before undergoing any study-related procedure and/or receiving study intervention), through and including approximately 90 days after the last administration of the study intervention or until study completion or withdrawal, whichever is longer.

Follow-up by the investigator continues throughout and after the active collection period and until the AE or SAE or its sequelae resolve or stabilize at a level acceptable to the investigator and Pfizer concurs with that assessment.

For participants who are screen failures, the active collection period ends when screen failure status is determined.

If the participant withdraws from the study and also withdraws consent for the collection of future information, the active collection period ends when consent is withdrawn.

If a participant definitively discontinues or temporarily discontinues study intervention because of an AE or SAE, the AE or SAE must be recorded on the CRF and the SAE reported using the CT SAE Report Form.

Investigators are not obligated to actively seek AE or SAE after the participant has concluded study participation. However, if the investigator learns of any SAE, including a death, at any time after a participant has completed the study, and he/she considers the event to be reasonably related to the study intervention, the investigator must promptly report the SAE to Pfizer using the CT SAE Report Form.

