8.3.1.2. Recording Nonserious AEs and SAEs on the CRF

All nonserious AEs and SAEs occurring in a participant during the active collection period, which begins after obtaining informed consent as described in [Section 8.3.1](#), will be recorded on the AE section of the CRF.

The investigator is to record on the CRF all directly observed and all spontaneously reported AEs and SAEs reported by the participant.

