## 6.6. Safety Summaries and Analyses

The safety endpoints are presented in the [Section 3.5](#). A set of summary tables split by treatment will be produced to evaluate any potential risk associated with the safety and toleration of administering vupanorsen.

No formal analyses are planned for safety data. The safety endpoints will be listed and summarized in accordance with the sponsor reporting standards, where the resulting data presentations will consist of participants from the safety analysis set.

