### 6.6.1. Adverse Events

Adverse events will be listed and summarized by treatment in accordance with the sponsor reporting standards.

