### 6.6.3. Vital Signs

Absolute values and changes from baseline in supine systolic and diastolic blood pressure and pulse rate will be summarized by treatment and postdose timepoints, according to the sponsor reporting standards. Tables will be paged by parameter. Baseline is as defined in Section 3.5.3.

Maximum increase or decrease in vital signs will also be summarized; all planned and unplanned postdose timepoints will be included in these summaries.

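### Could adverse events that began before dosing be counted under a dose because SAP 6.6.1 does not name the treatment-emergent flag?

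*SAP*

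**What the plan says.** SAP 3.5.1 sets the flag. An event is treatment-emergent if it starts on or after dosing but "before the last dose plus the lag time as defined in the protocol will be flagged as Treatment-Emergent Adverse Events (TEAEs"). A second sentence settles events that start on the day of dosing. The section says nothing else.

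SAP 6.6 opens by referring the reader to Section 3.5 for the safety endpoints. It then says that "summary tables split by treatment will be produced to evaluate any potential risk associated with the safety and toleration of administering vupanorsen", using participants in the safety analysis set and following the sponsor's reporting standards. SAP 6.6.1 is one sentence: "Adverse events will be listed and summarized by treatment in accordance with the sponsor reporting standards".

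On collection, Protocol 8.3.1 says the period "begins from the time the participant provides informed consent" and runs "through and including approximately 90 days after the last administration of the study intervention or until study completion or withdrawal, whichever is longer". If consent to further data collection is withdrawn, "the active collection period ends when consent is withdrawn". Protocol 8.3.1.2 sends to the CRF "All nonserious AEs and SAEs occurring in a participant during the active collection period, which begins after obtaining informed consent". Protocol 4.1 gives up to 28 days of screening, about 90 days of follow-up and 9 participants per cohort.

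**The concern.** The SAP builds a flag that separates pre-dose from post-dose events, but no output is told in so many words to use it. The CRF will hold events from screening, and the scheduled physical examinations, whose untoward findings can become adverse events, fall only at screening and Day -1. Elsewhere the SAP states the restriction: for the vital-sign extremes, "all planned and unplanned postdose timepoints will be included in these summaries", and SAP 6.6.4 likewise refers to postdose timepoints. Silence on adverse events could therefore be read as counting everything from consent.

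The end of the flag also looks open, because the SAP takes the lag time from a protocol that never uses that term.

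At stake is a secondary endpoint in a study without placebo, where counts per dose are read directly as the safety result. With 9 participants per cohort, one extra participant is visible in a table.

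**Working it through.** **1. Length of the collection window.** 28 + 90 = 118 days, which matches the stated total. The pre-dose share is at most 28/118 = 23.7%. That is the planned ceiling and assumes every participant uses the full screening period. Protocol Section 8 allows a longer gap after unexpected delays.

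**2. Which events the tables would use.** Read in sequence:

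- SAP 6.6 sends the reader to Section 3.5 for the endpoints.
- For adverse events, Section 3.5 contains only the treatment-emergent rule and its same-day tie-break.
- SAP 6.6 says the tables assess risk from giving the drug.
- SAP 6.6.1 defers layout to sponsor standards that are not in the documents.

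No sentence tells the analyst to put pre-dose events under a dose. The flag would have no purpose if the tables ignored it.

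**3. When the flag ends.** The protocol has one post-dose period for collecting adverse events, in 8.3.1. The 1-month interval in 8.2.4 concerns repeat laboratory tests, and the 21-week interval in 8.3.5.1 concerns pregnancy details. Neither is an adverse-event window. With 8.3.1 as the lag, the only mismatch is that the SAP says before the end and the protocol includes the end, about one boundary day. If an analyst instead used a bare 90 days, the cut would fall at Day 1 + 90 = Day 91. A Day 90 visit held at the end of its +5 day window falls on Day 95, so at most Days 91 to 95 would be affected.

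**4. Size if the flag were ignored.** The documents give no pre-dose event rate. Let p be the chance that a dosed participant has a pre-dose event (assumed 2%, 5%, 10%) and q the chance of a post-dose event (assumed 40%), taken as independent. A cohort's overall incidence rises by 1/9 = 11.1 points only for a participant with a pre-dose event and no post-dose event, which has probability p(1 − q).

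| Quantity | p = 2% | p = 5% | p = 10% |
|---|---|---|---|
| Participants of 18 with a pre-dose event, 18p | 0.36 | 0.90 | 1.80 |
| At least one such participant in the study, 1 − (1 − p)^18 | 30% | 60% | 85% |
| At least one such participant in a given cohort, 1 − (1 − p)^9 | 17% | 37% | 61% |
| At least one in the study who changes overall incidence, 1 − (1 − 0.6p)^18 | 20% | 42% | 67% |
| Same, in a given cohort, 1 − (1 − 0.6p)^9 | 10% | 24% | 43% |
| Expected rise in a cohort's incidence, 0.6p | 1.2 points | 3.0 points | 6.0 points |

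A higher post-dose rate shrinks the effect. Protocol 2.2.2.3.2 reports 83.3% of vupanorsen-treated patients with at least one event in Study CS2, which had repeated dosing over a longer period in patients. At q = 83.3% the expected rise, 0.167p, is 0.3, 0.8 or 1.7 points. Pre-dose and post-dose events clustering in the same people would shrink it further.

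**5. Who enters the tables.** Protocol 5.4 keeps screen-failure data out of the clinical database, and the safety set contains dosed participants only. Pre-dose events that lead to exclusion therefore never reach these tables.

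**The case for a change.** The strongest case for acting is that flagging events is not the same as limiting tables to them. The vital-sign and ECG sections cite the same sponsor standards and still write the postdose limit out, so a reader cannot confirm from the SAP alone which events are counted. In rows for individual event terms, a pre-dose event adds a participant to its row unless that participant also has the same event after dosing. The cushion in step 4 is weaker there, and the 17% to 61% chance per cohort is the more relevant figure. The remedy would be two sentences.

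Part of this stands. The SAP does not name the flag in 6.6.1, the lag-time reference has no target, and the sponsor standards cannot be inspected. The contrast with vital signs is weak, though. Those data have no emergent flag, so the limit has to be written there. The laboratory section, 6.6.2, also states no postdose limit and defers to standards, so silence is a drafting habit in this SAP and not a decision to pool pre-dose data. The row-level effect still needs both an assumed pre-dose rate and tables that ignore the flag, and the documents support neither.

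**Conclusion.** No change to the plan follows. The omission in SAP 6.6.1 is a detail that the cross-reference to Section 3.5 and the stated purpose of the tables already supply. The lag time is a clerical slip with one sensible reading, the Protocol 8.3.1 collection period, and on that reading about one boundary day is at issue.

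Any distortion requires the sponsor's tables to disregard a flag the SAP defines for them, which cannot be checked from the documents. Even then, the expected rise in a cohort's overall incidence is about 3 points at an assumed 5% pre-dose and 40% post-dose rate, and 1.2 to 6.0 points for pre-dose rates of 2% to 10%. The 11.1-point shift applies only when a participant has a pre-dose event and no post-dose one.

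The study tests no hypothesis, has no decision rule and plans no formal safety analysis. Adverse events are also listed, so a stray pre-dose event among about 18 participants could be traced.

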#### **3.5.2. Laboratory Data**

Safety laboratory tests will be performed as described in the protocol.

To determine if there are any clinically significant laboratory abnormalities, the hematological, clinical chemistry, urinalysis, and coagulation safety tests will be assessed against the criteria specified in the sponsor reporting standards. The assessment will not take into account whether each participant's baseline test result is within or outside the laboratory reference range for the particular laboratory parameters. Baseline will be the last predose measurement collected on Day -1.

#### **3.5.3. Vital Signs**

Supine blood pressure and pulse measurements will be taken at all time points listed in the Schedule of Activities given in the protocol. Baseline will be defined as the measurement obtained on Day 1 predose.

The maximum decrease and increase from baseline over all measurements taken postdose for supine systolic and diastolic blood pressures will be determined. The maximum increase from baseline will be calculated by first subtracting the baseline value from each postdose measurement to give the change from baseline. The maximum of these values over the entire study will then be selected, except in the case where a participant does not show an increase. In such an instance, the minimum decrease should be taken.

Similarly, the maximum decrease from baseline will be determined by selecting the minimum value of the change from baseline. In cases where a participant does not show a decrease, the minimum increase should be taken.

### 3.5.4. Electrocardiograms

Standard 12-lead ECGs will be taken at all time points listed in the Schedule of Activities given in the protocol. Baseline will be defined as the measurement obtained on Day 1 predose.

The QT, QTcF, PR, QRS and heart rate (HR) will be recorded at each assessment time.

If not supplied, QTcF will be derived using Fridericia's heart rate correction formula:

$$\text{QTcF} = \text{QT}/(\text{RR})^{1/3} \quad \text{where respiratory rate (RR)} = 60/\text{HR} \text{ (if not provided)}$$

The maximum absolute value (postdose) and the maximum increase from baseline will be determined over all measurements taken postdose for QTcF, PR and QRS.

The maximum increase from baseline will be calculated by first subtracting the baseline value from each postdose measurement to give the change from baseline. The maximum of these values over the entire study will then be selected, except in the case where a participant does not show an increase. In such an instance, the minimum decrease should be taken.

## 4. ANALYSIS SETS (POPULATIONS FOR ANALYSIS)

For purposes of analysis, the following analysis sets are defined:

Participant Analysis Set	Description
Enrolled	All participants who sign the informed consent document (ICD).
Pharmacokinetics (PK)	The PK concentration population is defined as all participants enrolled and treated who have at least 1 vupanorsen concentration. The PK parameter analysis population is defined as all participants enrolled and treated who have at least 1 of the vupanorsen PK parameters of interest.
Pharmacodynamics (PD)	The PD parameter analysis population is defined as all participants enrolled and treated who have at least 1 of the PD parameters of interest.
Safety	All participants enrolled and who take at least 1 dose of study intervention.

If a participant receives a treatment that is not consistent with the treatment they are assigned to, then the participant will be reported under the treatment that the participant actually received for all PK, PD and safety analyses, where applicable.

## **5. GENERAL METHODOLOGY AND CONVENTIONS**

The study will be analyzed and reported once all participants have completed the study (or discontinued), ie, following the data set release.

### **5.1. Hypotheses and Decision Rules**

There are no statistical hypotheses or decision rules.

### **5.2. General Methods**

All data will be descriptively summarized by treatment (vupanorsen 80 mg and 160 mg).

#### **5.2.1. Analyses for Binary Endpoints**

Binary endpoints will be summarized by treatment and visit (if appropriate) with number and percentage of participants in each category, if not otherwise specified.

#### **5.2.2. Analyses for Continuous Endpoints**

Continuous endpoints will be summarized by treatment and visit using descriptive statistics, including n, arithmetic mean, median, standard deviation (SD), minimum and maximum, if not otherwise specified.

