2.2.2.2. Clinical Pharmacodynamics

In the Phase 1 Study CS1, results from the SAD portion of the study showed dose dependent reductions in mean levels of serum ANGPTL3 protein at Day 15 (reductions of 5.5% to 80.2% for 20 to 120 mg). After 6 weeks of QW treatment, participants in the multiple-dose groups showed time- and dose-dependent reductions in mean levels of serum ANGPTL3 protein. The mean reductions of serum ANGPTL3 from baseline at Day 43 were 46.6% to 84.5% for 10 to 60 mg QW, ($P <0.01$ for all doses versus placebo).

PD was evaluated in a Phase 2a study (Study CS2) in participants with HTG, T2DM, and NAFLD. The maximum lowering of the circulating ANGPTL3 protein was observed at vupanorsen 80 mg Q4W (reductions of 62% from baseline), with a similar effect at vupanorsen 20 mg QW (reductions of 59% from baseline) and smaller effect at vupanorsen 40 mg QW (reductions of 45% from baseline).

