4.2. Scientific Rationale for Study Design

This study is the first clinical study with vupanorsen in the Chinese population. The purpose of the study is to characterize the PK, PD, safety and tolerability of vupanorsen following 80 mg and 160 mg subcutaneous dose in healthy male and female Chinese participants.

There is no expected significant PK difference between Chinese and Westerners because uptake/efflux-transporters, oxidative metabolism and conjugation, which may cause ethnic differences, are not involved in the disposition of ASOs. PK and PD parameters generated from this study will be compared with results from the global studies to further evaluate the impact of ethnicity/race on the PK/PD of vupanorsen.

Single-dose rather than repeated dosing is planned in the study as the steady-state PK and PD can be well predicted from single dose data, especially given that after QW multiple SC doses, the C_{max} and AUC increased approximately dose proportionally, and no apparent accumulation of C_{max} or AUC was observed. In terms of safety and tolerability, vupanorsen was well-tolerated with an acceptable safety profile at single doses up to 120 mg, and weekly repeated doses of up to 60 mg for 6 weeks in healthy participants in study CS1, and after repeated doses up to 80 mg per month (either 80 mg Q4W or 20 mg QW) for 6 months treatment duration in study CS2. The safety and tolerability of vupanorsen was consistent after single- and multiple-dose treatments except for the late onset of ADA (a median onset of 5.5 months) after multiple doses with no apparent impact on efficacy and safety, which is consistent with other ASOs in the same class. Moreover, considering the long terminal plasma half-life of vupanorsen in humans (3 to 5 weeks) and it will take approximately 21 weeks of vupanorsen dosing to reach steady-state, single-dose is planned to minimize the exposure duration of healthy participants to a new chemical entity.

The study duration and frequency of each assessment were decided based on information from previous studies. It was considered that 90 days are the necessary period to allow adequate characterization of terminal $t_{1/2}$ of vupanorsen to be eliminated. Sample collection points for PK were selected based on the results of PK profiles in Studies CS1 and CS2.

Serum ANGPTL3 and other lipid PD markers will be evaluated to confirm the target engagement of vupanorsen and the consistency with the results in Studies CS1 and CS2.

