**Table 3. PK Parameters to be Summarized Descriptively by Treatment**

Parameter	Summary Statistics
$C_{max}$ , $AUC_{24h}$ , $AUC_{48h}$ , $AUC_{last}$ , $AUC_{inf}$ , $CL/F$ , $V_z/F$	n, arithmetic mean, median, SD, minimum, maximum, percent coefficient of variation (%CV), geometric mean and geometric %CV
$T_{max}$	n, median, minimum, maximum
$t_{1/2}$	n, arithmetic mean, median, %CV, SD, minimum, maximum

There will be one summary table presenting all PK parameters.

To assess the relationship between the PK parameters and dose, box and whisker plot of dose normalized  $C_{max}$ ,  $AUC_{24h}$ ,  $AUC_{48h}$ ,  $AUC_{last}$ , and  $AUC_{inf}$  will be plotted against dose, and will include individual participant values and geometric means for each dose. Geometric means will have a different symbol than individual values. The values will be dose normalized (to 1 mg dose) by dividing the individual values and raw geometric means by dose. A footnote will be added to the plots to indicate that geometric means are presented.

The PK concentrations will be listed and summarized for participants in the PK concentration analysis set. Presentations for PK concentrations will include:

- A listing of all concentrations sorted by subject ID, treatment and nominal time postdose. The concentration listing will also include the actual times. Deviations from the nominal time will be given in a separate listing. The listing will be paged by treatment.
- A summary of concentrations by treatment and nominal time postdose, where the set of statistics will include n, mean, median, standard deviation, coefficient of variation (cv), minimum, maximum and the number of concentrations above the lower limit of quantification.
- Median concentrations time plots (on both linear and semi-log scales) against nominal time post dose by treatment (all treatments on the same plot per scale, based on the summary of concentrations by treatment and time postdose).
- Mean concentrations time plots (on both linear and semi-log scales) against nominal time post dose by treatment (all treatments on the same plot per scale, based on the summary of concentrations by treatment and time postdose).
- Individual concentration time plots by treatment (on both linear and semi-log scales) against actual time postdose. There will be separate spaghetti plots for each treatment per scale.

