### **6.2.2. Pharmacodynamic Endpoints**

The PD analysis will be conducted in the PD analysis set (as defined in [Section 4](#)). Non-fasting results will not be included in the analysis.

The baseline, the actual values, changes and percent changes from baseline in the following endpoints will be summarized by treatment and visit using descriptive statistics.

- ANGPTL3, TC, LDL-C, HDL-C, non-HDL-C, VLDL-C, TG, ApoA-I, ApoB total (including ApoB-48, ApoB-100), and ApoC-III.

Additionally, the following graphical summaries will be provided for the actual values, changes and the percent changes from baseline over time:

- Mean  $\pm$  SD by treatment and day (all treatments on the same plot);
- Individual plots against day (there will be separate plots for each treatment).

A listing for the actual values, changes and percent changes from baseline with fasting status sorted by treatment, subject ID and day will be presented.

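### Do the pharmacodynamic percent changes need a geometric mean and a confidence interval as well as the planned arithmetic mean, median and SD?

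*SAP*

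**What the plan says.** SAP 6.2.2 states that baseline, actual values, "changes and percent changes from baseline in the following endpoints will be summarized by treatment and visit using descriptive statistics". It names no statistics, so the default in SAP 5.2.2 applies: "using descriptive statistics, including n, arithmetic mean, median, standard deviation (SD), minimum and maximum". The list opens with the word including, so it does not bar additions.

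The group-level plot in SAP 6.2.2 is mean ± SD "by treatment and day (all treatments on the same plot"). The same section adds "Individual plots against day (there will be separate plots for each treatment") and a listing of each participant's values, changes and percent changes.

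On baseline, SAP 3.4 says: "Baseline variables are those collected on Day 1 prior to dosing or last measurement before Day 1". For PK exposure, clearance and volume, SAP Table 3 adds "percent coefficient of variation (%CV), geometric mean and geometric %CV", but no confidence interval there either.

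Protocol 4.2 gives the use of the results: "PK and PD parameters generated from this study will be compared with results from the global studies". Protocol 2.2.2.2 reports the earlier results as means, for example in CS1: "The mean reductions of serum ANGPTL3 from baseline at Day 43 were 46.6% to 84.5" percent. Protocol 9.1 and SAP 5.1 state that the study has no hypotheses; SAP 5.1 adds that it has no decision rules. PD is a secondary objective.

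**The concern.** A percent change is 100 × (post/baseline − 1), so its natural scale is multiplicative. For any positive ratios that are not all equal, the arithmetic mean exceeds the geometric mean. The average percent change therefore always shows a smaller reduction than the geometric one. Baseline is a single measurement, so its noise enters every ratio for that participant. With about 8 evaluable participants per cohort, one odd ratio can shift the plotted mean.

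The SAP recognises the multiplicative scale for PK and then appears not to apply it to PD. If lipid variability here differed from that in the global studies, the same true effect would give different arithmetic means, and part of an apparent ethnic difference could be an artefact of the summary. The lack of any presented interval also looks like an omission in a study of this size.

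**Working it through.** **Inputs.** From the documents: 8 evaluable participants per cohort (Protocol 9.2) and the statistics listed in SAP 5.2.2. The documents give no PD standard deviation and no expected lipid effect, so there is no planned figure to reproduce. Assumed: true post/baseline ratio R = 0.7 (a 30% fall), within-person CV of 10%, 20% or 30%, and independent lognormal noise in the baseline and post-dose values.

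**1. Size of the gap.** Under this model E[post/baseline] = R(1 + CV²), so the arithmetic mean percent change sits 100 × R × CV² points above the geometric one.
- R = 0.7: 70 × 0.01 = 0.7; 70 × 0.04 = 2.8; 70 × 0.09 = 6.3 points.
- R = 0.2 (an 80% fall, near the 80.2% upper end of the Day 15 ANGPTL3 reductions in Protocol 2.2.2.2): 0.2, 0.8 and 1.8 points.

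**2. What the planned median already does.** Simulation of 400,000 cohorts, n = 8, R = 0.7; all entries are percentage points measured against the geometric target of -30%.

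| CV | Bias: mean / median / geometric mean | RMSE: mean / median / geometric mean |
|---|---|---|
| 10% | 0.7 / 0.1 / 0.1 | 3.6 / 4.1 / 3.5 |
| 20% | 2.8 / 0.6 / 0.3 | 7.9 / 8.2 / 7.0 |
| 30% | 6.3 / 1.3 / 0.7 | 13.3 / 12.3 / 10.5 |

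The median removes most of the gap. The RMSE column also charges the mean for missing a target it does not estimate. Against its own target its error is √(13.3² − 6.3²) = 11.7 points at CV 30% and √(7.9² − 2.8²) = 7.4 points at CV 20%.

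**3. Outliers.** If each log ratio has a 10% chance of three times the SD, RMSE for mean / median / geometric mean is 14.8 / 8.9 / 9.5 at CV 20% and 38.0 / 13.5 / 14.4 at CV 30%. The mean suffers badly, but the planned median does slightly better than the geometric mean.

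**4. The interval.** A reader can form mean ± t × SD/√n from the planned table. At n = 8, t(7) = 2.365 and 2.365/√8 = 0.836, so the interval is mean ± 0.836 SD. Even against the geometric value of -30% it covers 95.0% of the time at CV 20% and at CV 30%. Its average width is 33.1 points against 32.1 for a log-scale interval (CV 20%), and 51.7 against 48.5 (CV 30%). Under the outlier model the average widths diverge (47.5 against 41.9; 86.8 against 64.7), but a few extreme cohorts drive that. The median widths are about 37 against 37 and 56 against 55.

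**5. Comparison across studies.** Two studies with the same true 30% fall differ in expected mean by 70 × (CV₁² − CV₂²): 0 at equal CV, 70 × (0.0625 − 0.04) = 1.6 points at 25% against 20%, and 70 × (0.09 − 0.04) = 3.5 points at 30% against 20%. The earlier ANGPTL3 results are means, so the planned mean is the matching statistic. No geometric PD comparator appears in either document.

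**The case for a change.** The best case for adding the log-scale summary is that it costs a few table rows and suits ratio data. If the log ratios are close to normal it is also more precise than the median: RMSE 7.0 against 8.2 at CV 20%, so the median is about 17% worse. Equal variability across studies is not assured, since CS2 enrolled patients with HTG, T2DM and NAFLD and this study enrols healthy adults. The only group-level plot shows the statistic most exposed to an outlier.

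The direction of the gap stands, and so does the precision gain under near-normal logs. Neither makes the plan deficient. The gain reverses under a modest outlier model. The mean ± SD plot does not stand alone: the median, minimum, maximum, individual plots and listing show when one participant drives the mean, and a geometric mean can be computed from the listing without new data. CS1, the other comparator, enrolled healthy participants, so unequal variability is a possibility for one comparator only.

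Nor do the documents single out a marker that needs this treatment. The repeat TG allowed at screening (Protocol 5.1, criterion 3) might suggest an unstable marker, but Protocol 5.2 also provides for repeats of blood pressure, ECG intervals and liver tests. It is an eligibility provision and tells us nothing specific about TG. Adding intervals has its own cost: TG alone would bring 7 visits × 2 cohorts = 14 unadjusted intervals.

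**Conclusion.** The concern does not hold. The arithmetic mean percent change is a valid summary of the average individual change, and it matches how the earlier ANGPTL3 results are reported. Its distance from the geometric change is 0.7 to 6.3 points for an assumed 30% fall at CV 10% to 30%, and 0.2 to 1.8 points for an 80% fall. The planned median leaves 0.1 to 1.3 points in the 30% case. These sizes rest wholly on assumed CVs and a lognormal model, because the documents supply no PD variance; a larger spread would widen the gap for the mean. Followed as written, the SAP gives sound descriptive PD results from which a reader can judge both the typical change and its precision. No hypothesis or decision rule depends on the choice, so nothing needs to change.
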